3. SHOCK WAVE MACHINE AND PROCEDURES

The shock wave applicator (“LITEMED” LM-ESWT-mini system, Taiwan) will be gently placed directly on the ultrasound transmission gel over the skin surface of suprapubic region above the urinary bladder during once a week for 4 weeks, with 2000 shocks, frequency of 3 pulses per second, and maximum total energy flow density 0.25 mJ/mm^2 . The current shock wave intensity and number used was modified from previous report [1, 2].

Eligible patients will be assigned a randomization number in sequential order and each of the randomization will determine the allocation of one of the two treatment groups (LESW and Placebo) in 1: 1 ratio as shown below. The LESW and placebo will be controlled by a research assistance who will not evaluate the therapeutic outcome to ensure the double-blind method.

Vital signs (body temperature, blood pressure, heart rate and respiration rate) will be recorded at pre-treatment and 30 minutes following treatment.

The treatment will be carried out in the out-patient clinic. Patient will be stayed in a treatment room and accompanied by a research assistant.

3.1. Randomization

Permuted block randomization method will be applied to generate randomization codes. Each randomization number will be assigned to individual patient according to the time-sequence for screened patient become eligible.

3.2. Blinding

The blinding of the study is double blind to the investigator and patients. The placebo treatment was performed with the same therapy head, which was also fitted with a placebo stand-off. This stand-off contained shock wave-absorbing material, a layer of air, and air-filled microspheres [1]. Performance of the placebo stand-off was validated by measuring the output pressure in a laboratory setup. The setting was identical to the verum treatment. The blinding included the specification that neither the patient nor the investigator/follow-up observer was aware of placebo or verum assignment.

4. SUBJECTS

4.1. Number and Source

Approximately 50 patients will be enrolled and be completed within the two-year study period.

4.2. Inclusion Criteria

Patients must meet all the following criteria to be eligible to enter the trial:

- 4.2.1. Adults with age of 20 years old or above.
- 4.2.2. Patients with symptoms of unpleasant sensation (pain, pressure, discomfort) perceived to be related to the urinary bladder, associated with lower urinary tract symptoms of more than six months duration, in the absence of infection or other identifiable causes.
- 4.2.3. Patients has received cystoscopy and ruled out other bladder lesion.
- 4.2.4. Free of active urinary tract infection.
- 4.2.5. Free of bladder outlet obstruction on enrollment.
- 4.2.6. Free of overt neurogenic bladder dysfunction and limitation of ambulation.
- 4.2.7. Patient or his/her legally acceptable representative has signed the written informed consent form.

4.3. Exclusion Criteria

- 4.3.1. Patients had received intravesical hyaluronic acid treatment in recent 3 months, or intravesical Botox injection in recent 12 months. Patients with severe cardiopulmonary disease and such as congestive heart failure, arrhythmia, poorly controlled hypertension, not able to receive regular follow-up.
- 4.3.2. Patients with bladder outlet obstruction on enrollment.
- 4.3.3. Patients with PVR >100 ml.
- 4.3.4. Patients with uncontrolled confirmed diagnosis of acute urinary tract infection.
- 4.3.5. Patients have laboratory abnormalities at screening including:
 - ALT > 3 x upper limit of normal range.
 - AST > 3 x upper limit of normal range.
- 4.3.6. Patients have abnormal serum creatinine level > 2 x upper limit of normal range.
- 4.3.7. Female patients who is pregnant, lactating, or with child-bearing potential without contraception.

- 4.3.8. Patients with any other serious disease considered by the investigator not in the condition to enter the trial.
- 4.3.9. Patients had received intravesical treatment for IC within recent 1 month.
- 4.3.10. Patients had participated investigational drug trial within 1 month before entering this study.
- 4.3.11. Patients with coagulopathy.

5. STUDY PROCEDURE

5.1. General Study Design

This study is designed as a double-blind, randomized, paralleled, controlled trial. The IC/BPS confirmed patients will be randomly assigned to receive (1) LESW or (2) placebo control group. The treatments will be evaluated at baseline screening and at least 2 study required visits (treatment visit and primary end-point evaluation visit) will be performed for symptom score recording, VAS, uroflowmetry studies, adverse event recording and global satisfaction assessments. Urine samples (30 ml) will also be collected at each visit for analysis of the urinary NGF and cytokines levels.

Procedures of LESW

Studied patients are requested to void completely before treatment. Urine samples (30 ml) will be collected for analysis of the urinary NGF and cytokines levels. The patients are placed in supine position in an examination room at out-patient clinic.

The shock wave applicator (“**LITEMED**” **LM-ESWT-mini system, Taiwan**) will be gently placed directly on the ultrasound transmission gel over the skin surface of suprapubic region above the urinary bladder weekly for 4 weeks, with 2000 shocks, frequency of 3 pulses per second, and maximum total energy flow density 0.25 mJ/mm². The current shock wave intensity and number used was modified from previous report [1, 2].

Patients will be asked about any painful sensation that they experience during the treatment. Vital signs (body temperature, blood pressure, heart rate and respiration rate) will be recorded at pre-treatment, and 30 mins following treatment. During the treatment, patient will be stayed in a treatment room and accompanied by a research assistant.

5.2. Study Visits and Evaluations

5.2.1. Screening Visit (2 weeks before the treatment day)

5.2.1.1 Explain the nature of the study and have patients to read and sign an Informed Consent Form.

5.2.1.2 Screen patients for inclusion/exclusion criteria (section 4.2 and 4.3).

5.2.1.3 Medical History of IC/BPS and previous treatment modalities.

5.2.1.4 Vital signs monitoring and general physical examinations of all systems, EKG examination to rule out abnormal cardiac diseases, and biochemistry examinations including CBC, PT, APTT, ALT, AST and Cr.

5.2.1.5 Check Uroflowmetry and record, maximum flow rate, voided volume and PVR volume.

5.2.1.6 Urinalysis for WBC, RBC, PH, Protein, Glucose, Bacteria if patient has symptoms suggestive of urinary tract infection.

5.2.1.7 Physical assessments to exclude bladder outlet obstruction or bladder pathology.

5.2.1.8 Record concomitant medication.

5.2.1.9 Dispense three-day voiding diary to record for 3 days before the treatment day.

5.2.1.10 Record O'Leary-Sant symptom score, VAS.

5.2.1.11 Discontinue all previous IC-related medication.

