2. OBJECTIVE AND ENDPOINTS

The objective of this study is to evaluate the efficacy and safety of LESW for the treatment of IC/BPS.

The primary and secondary endpoints are described as shown below:

(1) Primary End-point (1 month)

The efficacy of LESW will be evaluated for:

Net changes of the O’Leary-Sant symptom score from baseline to 1 month after the treatment day.

(2) Secondary end-points

Efficacy

The efficacy of LESW will be evaluated for:

- (1) Net changes of the following parameters from baseline to 1 month after the treatment day: VAS, functional bladder capacity (FBC), voiding frequency at daytime and voiding frequency at night time as recorded in 3-day voiding diary.
- (2) Global response assessment (GRA) of therapeutic result by the patient (categorized from -3 to +3, indicating markedly worse to markedly improved) at 3 months after the treatment day.
- (3) Net changes of the maximum flow rate, voided volume, and PVR from baseline to 1 month after the treatment day.

(4) Changes of urinary nerve growth factor and cytokines level from baseline to 1 month after treatment day.

Effectiveness of treatment was considered if the patient has an improved GRA by 2 scales at the end-point assessments.

Safety

(1) Local adverse event incidences (hematuria, miction pain, UTI, urinary retention). The severity of adverse event is categorized as indicated below:

Severity of AE	Description
Mild	Transient and easily tolerable, not affecting usual daily activities
Moderate	Causes patient's discomfort, interrupting usual daily activities
Severe	Causes considerable interference with daily activities and may be incapacitating or life-threatening

(2) Systemic Adverse Events:

Any systemic adverse event occurring after LESW will be asked to report and patients will be properly investigated and treated. The cause for systemic adverse event may be not related with LESW.

(3) Changes in physical examinations.

(4) Changes in blood pressure and other laboratory test results will be examined if patients have severe adverse events or physical examinations reveal abnormalities.

(3) Follow-up (3 months)

Efficacy

The efficacy of LESW will be evaluated for:

- (1) Net changes of the following parameters from baseline to 1 month after the treatment day: VAS, functional bladder capacity (FBC), voiding frequency at daytime and voiding frequency at night time as recorded in 3-day voiding diary.

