5.2.2. Randomization and Treatment Visit (V1, Week 0)

5.2.2.1 Vital signs monitoring, check EKG and biochemistry results and confirm eligibility of patients.

5.2.2.2 A randomization number is given to eligible patient.

5.2.2.3 Inform patient of the possible adverse events.

5.2.2.4 Review three-day voiding diary.

5.2.2.5 Collect 30 ml urine for analysis of the urinary NGF and cytokines levels.

5.2.2.6 LESW given.

5.2.3. Treatment Visit (V2, Week 1, 1 week \pm 3 days after the V1 treatment day)

5.2.3.1 Vital signs monitoring, and confirm eligibility of patients.

5.2.3.2 LESW given.

5.2.4. Treatment Visit (V3, Week 2, 1 week \pm 3 days after the V2 treatment day)

5.2.4.1 Vital signs monitoring, and confirm eligibility of patients.

5.2.4.2 LESW given.

5.2.5. Treatment Visit (V4, Week 3, 1 week \pm 3 days after the V3 treatment day)

5.2.5.1 Vital signs monitoring, and confirm eligibility of patients.

5.2.5.2 LESW given.

5.2.5.3 Dispense three-day voiding diary to record for 3 days before the next visit day.

5.2.6 Evaluation Visit I (V5, 1 week \pm 3 days after the V4 treatment day)

5.2.6.1 Review patients voiding diary for urinary frequency, functional bladder capacity, and record reported VAS, O'Leary-Sant symptom score, and GRA.

5.2.6.2 Vital signs monitoring and record adverse events.

5.2.6.3 Check urinalysis for urinary tract infection if patient has symptoms.

5.2.6.4 Check uroflowmetry for maximum flow rate, voided volume, and PVR volume.

5.2.6.5 Appointment for the next visit at 1 month \pm 3 days after the V4.

5.2.6.6 Dispense three-day voiding diary to record for 3 days before the next visit day.

5.2.6.7 Collect 30 ml urine for analysis of the urinary NGF and cytokines levels.

5.2.7 Evaluation Visit II (Primary end-point, V6, 1 month \pm 7 days after the V4)

5.2.7.1 Review patients voiding diary for urinary frequency, functional bladder capacity, and record reported VAS, O'Leary-Sant symptom score, and GRA.

5.2.7.2 Vital signs monitoring and record adverse events.

5.2.7.3 Check urinalysis for urinary tract infection if patient has symptoms suggestive of urinary tract infection.

5.2.7.4 Perform Uroflowmetry study for maximum flow rate, voided volume and PVR volume.

5.2.7.5 Collect 30 ml urine for analysis of the urinary NGF and cytokines levels.

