5.2.8 Evaluation Visit III (V7, 3 month \pm 7 days after the V4)

5.2.8.1 Review patients voiding diary for urinary frequency, functional bladder capacity, and record reported VAS, O'Leary-Sant symptom score, and GRA.

5.2.8.2 Vital signs monitoring and record adverse events.

5.2.8.3 Check urinalysis for urinary tract infection if patient has symptoms suggestive of urinary tract infection.

5.2.8.4 Perform Uroflowmetry study for maximum flow rate, voided volume and PVR volume.

5.2.8.5 Collect 30 ml urine for analysis of the urinary NGF and cytokines levels.

5.2.8.6 Patients who do not respond to treatment will be provided with repeat LESW treatment optionally.

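### Symptom-triggered urinalysis leaves infection-free entry unassured and makes UTI detection after treatment depend on symptom response

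*Protocol*

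**What the plan says.** **Entry.** Protocol 4.2.2 requires bladder discomfort "associated with lower urinary tract symptoms of more than six months duration, in the absence of infection or other identifiable causes". Section 4.2.4 adds "Free of active urinary tract infection", and 4.3.4 excludes "Patients with uncontrolled confirmed diagnosis of acute urinary tract infection". None of the three names a test. At V1 (5.2.2.1) eligibility is confirmed from EKG and biochemistry; no urine result is listed.

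**Testing.** The only scheduled infection test is conditional:
- Screening (5.2.1.6): "Urinalysis for WBC, RBC, PH, Protein, Glucose, Bacteria if patient has symptoms suggestive of urinary tract infection".
- V5 (5.2.6.3): "Check urinalysis for urinary tract infection if patient has symptoms", with no qualification of which symptoms.
- V6 (5.2.7.3) and V7 (5.2.8.3): "Check urinalysis for urinary tract infection if patient has symptoms suggestive of urinary tract infection".

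No urinalysis is listed at V1 to V4. RBC is named only for the screening urinalysis.

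**Safety endpoint.** Protocol section 2 lists "Local adverse event incidences (hematuria, miction pain, UTI, urinary retention") as a safety endpoint. SAP 7.2 reports these incidences for each group and plans a between-treatment analysis, with no test or denominator stated. Adverse events are recorded at V5, V6 and V7 without a symptom condition.

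**Urine already taken.** At V1 (5.2.2.5) the protocol lists "Collect 30 ml urine for analysis of the urinary NGF and cytokines levels". The same item appears at V5, V6 and V7.

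**The concern.** The trigger does not separate infection from the disease under study. A patient with chronic bladder discomfort and urinary symptoms may or may not be judged to meet it. The protocol leaves that to each investigator, in wording that changes between visits. A patient can therefore be entered as infection-free without a urine test. The per-protocol set in SAP 7.1 requires all entry criteria to be met, and for 4.2.4 this cannot be checked objectively in an untested patient.

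After treatment the problem is ascertainment. Whether a patient is tested depends on symptoms, and symptoms are also what the primary endpoint measures. If LESW works, fewer LESW patients meet the trigger and fewer of their infections are found. Blinding does not prevent this, because the path runs through the patient's response and not through knowledge of the allocation. The same holds for microscopic hematuria, if the endpoint is meant to include it.

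Protocol 6.1 adds to the difficulty. A deterioration that could be either an adverse event or lack of efficacy is by default counted as lack of efficacy, so an untested infection that worsens bladder symptoms may never be recorded as a UTI.

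**Working it through.** The documents give no rate for UTI, hematuria or urinalysis, so there is no figure of the plan's own to reproduce on this point. The sample size in SAP 7.4 is a separate matter. Only its planned response and group size are used here.

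**Inputs from SAP 7.4:** mean decrease in O'Leary-Sant score 8.0 (LESW) and 5.0 (placebo), SD 5.0, 25 patients per arm.

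**Assumptions (not in the documents):** decreases are normally distributed; a patient is tested at a visit if the decrease is below a threshold c; true UTI risk is equal in both arms; in the basic case, infection does not itself change the chance of being tested.

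**Step 1. Chance of being tested.** P(tested) = Φ((c − mean)/SD). At c = 6.5 this is Φ(−0.3) = 0.382 for LESW and Φ(0.3) = 0.618 for placebo.

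**Step 2. Detection ratio.** At equal true risk the risk cancels, so the LESW/placebo ratio of detected UTI is P(LESW)/P(placebo).

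**Step 3. Distinctly symptomatic infections.** If a share s of UTIs is tested whatever the score, the ratio is [s + (1 − s)P(LESW)] / [s + (1 − s)P(placebo)]. At c = 6.5 and s = 0.5 this is 0.691/0.809 = 0.85.

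| c (points) | P(tested) LESW | P(tested) placebo | Ratio, s = 0 | Ratio, s = 0.5 | Ratio, s = 0.8 |
|---|---|---|---|---|---|
| 0 | 0.055 | 0.159 | 0.35 | 0.91 | 0.98 |
| 3 | 0.159 | 0.345 | 0.46 | 0.86 | 0.96 |
| 5 | 0.274 | 0.500 | 0.55 | 0.85 | 0.95 |
| 6.5 | 0.382 | 0.618 | 0.62 | 0.85 | 0.95 |
| 8 | 0.500 | 0.726 | 0.69 | 0.87 | 0.95 |
| 10 | 0.655 | 0.841 | 0.78 | 0.90 | 0.96 |

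If LESW has no effect on the triggering symptoms, the two probabilities are equal and the ratio is 1.00 in every row.

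**Step 4. Expected counts at c = 6.5, s = 0.** Detected cases = 25 × risk × P(tested).

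| Assumed true risk | LESW detected | Placebo detected | Per arm if all tested |
|---|---|---|---|
| 5% | 0.48 | 0.77 | 1.25 |
| 10% | 0.96 | 1.54 | 2.50 |
| 20% | 1.91 | 3.09 | 5.00 |

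The gap between arms is widest at this threshold. Even at 20% risk it is 3.09 − 1.91 = 1.18 patients.

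**Step 5. Entry.** Expected undetected infections among 50 patients = 50 × prevalence × (1 − share tested). For assumed prevalences of 2%, 5% and 10% this gives 1.0, 2.5 and 5.0 if nobody is tested; 0.5, 1.25 and 2.5 if half are tested regardless of infection; and 0 if all are tested.

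**The case against.** The strongest reply has four parts.

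1. *Entry may in fact be checked.* A reader might infer that every IC/BPS patient has UTI-like symptoms by definition and that entry is therefore never verified. The documents do not support this. Section 4.2.2 requires chronic discomfort with urinary symptoms, not symptoms pointing to infection. If every patient did meet the trigger, 5.2.1.6 would order urinalysis for everyone. An investigator may also tell a new change from a chronic state. This stands: the supportable statement is that verification is not assured. Any infection missed at entry precedes randomization, so it is expected to add noise rather than bias by arm.

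2. *Hematuria does not depend on urinalysis as a whole.* Visible hematuria can be recorded as an adverse event at V5, V6 and V7 without a urine test. This stands. Only microscopic hematuria depends on the test, and the documents do not say whether the endpoint includes it.

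3. *Infected patients tend to have symptoms and so to be tested.* This largely stands as to size. It moves the ratio from 0.35–0.78 to 0.85–0.91 (s = 0.5) or 0.95–0.98 (s = 0.8). It does not remove the dependence on symptoms, and the default in 6.1 works against correct classification of ambiguous cases.

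4. *The primary result at V6 is not shown to be distorted.* A reader might infer that untested infections corrupt the V6 score. But an infection that raises symptoms is the kind that meets the trigger, so that argument conflicts with the mechanism proposed here.

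**Conclusion.** The point holds in a limited form. The testing rule does not assure freedom from infection at entry for every randomized patient, and after treatment it ties UTI detection to persisting symptoms. A tilt toward LESW arises only if LESW relieves the triggering symptoms, which is what the trial sets out to show. Otherwise the result is under-counting alone.

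The size is uncertain because the threshold, the true risk and the share of distinctly symptomatic infections are all assumed. Across those assumptions the detection ratio runs from 0.35 to 0.98. At true risks of 5% to 20% the gap is at most about 1.2 patients in 25. That is too few to settle a safety comparison either way, but with so few events, one or two missed cases would change the reported picture. This is a weakness in a secondary safety endpoint and in the documentation of eligibility. It should be changed because the rule itself produces outcome-dependent ascertainment and a better rule is cheap.

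**What to change.** 1. Remove the symptom condition. Do the urinalysis already listed in 5.2.1.6 in every patient before randomization, and again at V5, V6 and V7.
2. For the entry test, use screening, where the patient already voids for uroflowmetry, or V1 urine. If V1 is chosen, collection must move ahead of the randomization number, because 5.2.2.5 now follows 5.2.2.2. List the urine result in the V1 eligibility check.
3. At V5, V6 and V7, use the 30 ml specimen already taken. The documents do not say whether that volume serves both purposes, so confirm this with the laboratory.
4. State in advance how UTI is defined, which result fails 4.2.4, and whether hematuria includes microscopic findings.
5. In SAP 7.2, report UTI by arm with the number tested as denominator. List asymptomatic laboratory findings separately from clinical adverse events.

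If universal testing is declined, the minimum is to define the trigger in the same words at every visit, make the definitions in item 4, and report the number tested by arm and visit. That shows any imbalance but does not remove it.

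The cost is a protocol amendment and at most 4 × 50 = 200 inexpensive urinalyses, fewer in addition to those already done for symptoms. The downside is some incidental asymptomatic findings to document. With everyone tested, the detection ratio at equal true risk is 1.00 whatever LESW does to symptoms.

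### In the visit schedule, the only pre-treatment O'Leary-Sant, VAS and uroflowmetry values are taken at the visit where IC medication is stopped; used as baseline, they put any stopping effect into the within-arm results, but do not bias the between-arm test

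*Protocol*

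**What the plan says.** Protocol 5.2.1 is headed "Screening Visit (2 weeks before the treatment day" and closing bracket. Three of its items matter here:

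- 5.2.1.5: "Check Uroflowmetry and record, maximum flow rate, voided volume and PVR volume"
- 5.2.1.10: "Record O'Leary-Sant symptom score, VAS"
- 5.2.1.11: "Discontinue all previous IC-related medication"

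The item list for V1 (5.2.2.1 to 5.2.2.6) contains none of these measurements. It does contain the allocation step, "A randomization number is given to eligible patient", and a urine sample, "Collect 30 ml urine for analysis of the urinary NGF and cytokines levels". V2 to V4 list no scores or uroflowmetry either. All of these measures return at V5, V6 (the primary endpoint visit) and V7.

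The voiding diary is handled differently. It is handed out at screening but filled in later: "Dispense three-day voiding diary to record for 3 days before the treatment day".

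Protocol 5.1 refers to screening as the baseline assessment. It then says that the treatment visit and the primary endpoint visit serve for symptom score, VAS and uroflowmetry, among other things. SAP 7.1 also ties the word baseline to screening. Neither protocol section 2 nor SAP 7.2 says which visit supplies the baseline value.

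SAP 7.2 plans three things for net change: a paired t-test within each arm, an ANOVA between arms, and point estimates with 95% CIs for all efficacy variables. Protocol 5.4 bars a list of IC-related drugs during the study.

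**The concern.** If the schedule is followed, the starting value of the primary endpoint is taken while patients may still be on IC medication, and every later value is taken off it. The change within an arm then has at least three components besides any effect of the shock waves: placebo response, natural course, and the effect of stopping medication. The first two are present whatever the baseline. The third is there only because of where the baseline is placed.

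The planned within-arm paired t-tests and CIs are at stake for O'Leary-Sant, VAS, maximum flow rate, voided volume and PVR. The diary items (functional bladder capacity, day and night frequency) and the urine markers start after the stop, so changes reported side by side would have different starting conditions.

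The second difficulty is that 5.1 and 5.2.2 disagree on whether the treatment visit includes these measurements. A site that follows 5.1 would produce two pre-treatment scores for some patients, with no rule for which one counts.

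**Working it through.** **Step 1. Order of events under 5.2.**

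| Measure | Last pre-treatment value | Relative to the stop |
|---|---|---|
| O'Leary-Sant, VAS | Screening (5.2.1.10) | At the same visit, listed before it |
| Maximum flow rate, voided volume, PVR | Screening (5.2.1.5) | At the same visit, listed before it |
| Diary items | 3 days before V1 (5.2.1.9) | After |
| Urine NGF, cytokines | V1 (5.2.2.5) | After |
| All follow-up values | V5 to V7 | After |

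The randomization number is given at V1 (5.2.2.2), also after the stop.

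**Step 2. The plan's own figures.** SAP 7.4 gives decreases of 8.0 and 5.0, SD 5.0, α = 0.05, power 0.80 and 25 per group; SAP 7.2 makes tests two-sided. For two groups, n per group = 2 × (1.960 + 0.842)² × 5.0² / 3.0² = 43.6, so 44. The stated 25 does not reproduce. At 25 per group, the two-sample t-test has power 0.547. That is a separate matter; 0.547 is used below only as the reference value.

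**Step 3. Planned within-arm interval for O'Leary-Sant.** Taking SD 5.0 as the SD of change:

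- SE = 5.0 / √25 = 1.0
- t(0.975, 24 df) = 2.064, so the half-width is 2.06
- Treatment arm: 8.0 ± 2.06 = 5.94 to 10.06
- Control arm: 5.0 ± 2.06 = 2.94 to 7.06

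**Step 4. Effect of a stopping shift within an arm.** The documents give no size, no sign and no share of patients on medication, so m, the mean shift, is assumed. A shift common to all patients moves the whole interval by m. If the target is taken to be the change free of the stopping effect, the nominal 95% CI covers it with probability P(|T| < 2.064), where T is noncentral t with 24 df and noncentrality m / 1.0:

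| Assumed m (either sign) | Share of half-width | Coverage |
|---|---|---|
| 0.25 | 12% | 94.3% |
| 0.5 | 24% | 92.3% |
| 1 | 48% | 83.9% |
| 2 | 97% | 51.6% |

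**Step 5. Effect between arms.** A shift with the same distribution in both arms cancels in expectation. With +2 points in all patients, the changes become −6 and −3, and the difference stays −3.0. In simulations (25 per arm, SD 5, 40,000 runs per scenario), type I error was 4.9% to 5.1% across shifts of 0, ±2 in half the patients, +4 in half, and +2 or +4 in all.

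Precision can suffer if only some patients shift. Assume that half shift by s points, independently of the rest of their change, and that SD 5.0 does not already include this. The variance becomes 25 + s²/4:

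| s | SD | Power, 25 per arm |
|---|---|---|
| 0 | 5.00 | 0.547 |
| 1 | 5.02 | 0.543 |
| 2 | 5.10 | 0.531 |
| 4 | 5.39 | 0.488 |

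If SD 5.0 already includes the effect, nothing is lost against plan.

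**The case against.** **The trial's claim is superiority to placebo, tested between arms.** Within-arm changes cannot support that claim under any baseline, because placebo response and natural course remain in them. This stands, and it limits the weight of the point.

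**Section 5.1 may already provide a V1 score.** A score taken at the treatment visit before the shock waves, and used as baseline, would fall about 2 weeks after the stop and largely remove the problem. But 5.1 does not say that the score precedes treatment, and the detailed V1 list omits it. The conclusion is therefore conditional on a screening baseline. If 5.2 is followed, the case of two competing scores does not arise.

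**The coverage figures use a target that the SAP does not set.** Its quantity is the change from baseline to 1 month, and with a screening baseline the interval covers that quantity at its nominal rate. This stands: the table in step 4 shows what happens if the change is read as free of the stopping effect, and it does not show an error in the interval itself.

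**Recent intravesical treatment is already excluded** (4.3.1 and 4.3.9). That narrows the point to the remaining, mainly non-intravesical, medication.

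A reader might go further and infer that the treatment comparison is biased, or that every efficacy item in 7.2 is affected. The documents support neither. The stop comes before randomization and applies to both arms, and the diary items start after it.

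**Conclusion.** The point holds in a limited form and is minor. Sections 5.1 and 5.2.2 disagree on whether symptom score, VAS and uroflowmetry are recorded at the treatment visit, and the baseline visit is suggested but never stated. With a screening baseline, the within-arm changes, CIs and paired t-tests for O'Leary-Sant, VAS, maximum flow rate, voided volume and PVR include any effect of stopping medication. Diary items and urine markers do not have this problem.

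The between-arm ANOVA is unbiased and keeps its type I error. It can only lose precision, and in the illustrations the loss of power runs from 0.004 (1 point in half the patients) to 0.059 (4 points in half). These figures rest on assumed shifts, on independence from the rest of the change, and on SD 5.0 excluding the shift. The actual size and direction cannot be derived from the documents.

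**What to change.** 1. Reconcile 5.1 with 5.2.2. Add recording of O'Leary-Sant and VAS to 5.2.2, placed before step 5.2.2.2 so that the values precede allocation.
2. State in protocol section 2 and SAP 7.2 that the V1 value is the baseline for both measures, and report the screening value descriptively. No entry criterion in 4.2 or 4.3 uses either score, so eligibility is unchanged.
3. State the baseline visit for maximum flow rate, voided volume and PVR. The screening PVR is still needed for exclusion 4.3.3.
4. If patients have already been randomized without a V1 score, fix the screening score as baseline for all patients before unblinding, and describe the within-arm changes as including any effect of stopping medication. This needs no new data. Prior IC medication, available from "Medical History of IC/BPS and previous treatment modalities" (5.2.1.3) and the medication record (5.2.1.8), could be added as a prespecified covariate. This is optional: the medication is heterogeneous, so a yes/no term would recover only part of any lost precision.

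The cost is one short questionnaire and one VAS at an existing visit, plus a few sentences in the two documents. The limitation is that a V1 baseline removes the stopping effect only as far as that effect is complete by V1 and the questionnaire's recall period falls after the stop. The documents give neither.
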